9.4. Vital Signs

9.4.1. Vital Sign Parameters

Vital signs including heart rate, systolic blood pressure (SBP), diastolic blood pressure (DBP), weight, height, and body temperature will be measured according to Schedule of Assessments in Appendix 1.

Baseline vital signs refers to the most recent measurements taken prior to the first dose (pre-dose C1D1). Post-baseline assessments refer to the measurements taken after the first dose of any study drug and during treatment period. Change from baseline to the highest/lowest value across all post-baseline measurements for each vital sign parameter will be calculated. Patients with a non-missing baseline and at least one non-missing measurement post-first dose for a given parameter will be included in the calculation.

Patients are classified with respect to the criteria of potentially clinically significant (PCS) findings of vital signs, which are defined by the highest/lowest value among post-baseline assessments and/or the change from baseline to the highest/lowest observed value. Details of PCS criteria for vital signs can be found in Table 10.

Parameter	Direction	Highest/Lowest Observed Value	Change from Baseline to the Highest/Lowest Observed Value
SBP	High	≥180 mmHg	Increase ≥40 mmHg
	Low	\leq 90 mmHg	Decrease ≥40 mmHg
DBP	High	≥105 mmHg	Increase ≥ 20 mmHg
	Low	$\leq 50 \text{ mmHg}$	Decrease ≥20 mmHg
Heart Rate	High	≥ 120 bpm	Increase ≥40 bpm
	Low	\leq 50 bpm	Decrease ≥40 bpm
Weight	High		Increase ≥10%
	Low		Decrease ≥10%

 Table 10
 Criteria for Potentially Clinically Significant Vital Signs

bpm=beats per minute; DBP=diastolic blood pressure; SBP=systolic blood pressure

9.4.2. Analysis for Vital Signs

Number and percentage of patients who meet any PCS criteria for each vital sign parameter as well as for each criterion will be summarized.

All observed vital sign values, change from baseline at each post-first dose assessment, and PCS flag will be listed.

9.5. 12-lead Electrocardiograms

9.5.1. Electrocardiograms Parameters

The standard 12-lead Electrocardiogram (ECG) will collect heart rate, PR interval, QRS interval, RR interval, and QT interval at the frequency according to Schedule of Assessments in Appendix 1. Investigator's clinical interpretation of 12-lead ECG results by normal or abnormal will also be collected.

Since either QTcF or QTcB could be collected by different study sites, QTcF (using Fridericia's method) will be calculated from the QT and RR (converted from collected ms to sec) intervals based on the formula:

 $QTcF = Uncorrected QT/ (RR Interval)^{1/3}$, if QT and/or RR are missing, the QTcF will be left as missing.

Change from baseline to the highest/lowest value across all post-baseline measurements for QTcF will be calculated. Patients who had a non-missing baseline and at least one non-missing measurement post-first dose will be included in the calculation.

The potentially clinically significant ECG findings are defined by the highest/lowest value across all post-baseline assessments while during the treatment period for all parameters except for QTcF, for which both observed values and change scores are used to define the PCS findings (Table 11). For QTcF, a total of 5 different criteria are defined; some criteria are mutually exclusive and some cumulative (denoted by Criterion Index in Table 11).

ECG Parameter	Direction or Criterion Index	Highest/Lowest Observed Value	Change from Baseline to the Highest/Lowest Observed Value
RR Interval	High	> 1200 ms	
	Low	< 500 ms	
PR Interval	High	\geq 210 ms	
QRS Interval	High	≥ 120 ms	
	Low	\leq 50 ms	
QT Interval	High	\geq 500 ms	
	Low	\leq 300 ms	
QTcF	Index 1 (mutually exclusive)	≥ 500 msec	
		\geq 480 and < 500 msec	
		\geq 450 and < 480 msec	
		\leq 300 msec	
	Index 2	\geq 480 msec	
	Index 3	\geq 450 msec	
	Index 4 (mutually exclusive)		Increase ≥ 60
			Increase \geq 30 and $<$ 60 ms
	Index 5		Increase $\geq 30 \text{ ms}$

 Table 11
 Criteria for Potentially Clinically Significant ECG Findings

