9. SAFETY ANALYSIS

9.1. General Consideration of Safety Analysis

Safety data summaries will be based on the safety population as defined in Section 3.3 of this SAP.

Safety data collected during treatment will be summarized at the final analysis.

Safety and tolerability will be assessed by AEs, laboratory tests, vital signs and ECG. Safety data will be summarized using descriptive statistics for all patients when appropriate. All safety data collected through scheduled and non-scheduled visits during the treatment period will be included in the safety data analyses. The treatment period for a patient is defined as the time interval from date of C1D1 to the date of End of Treatment (EOT) visit. If the EOT visit does not occur for the patient, then 14 days post the last dose in the last cycle will be used as the end date of treatment. Missing safety data will generally not be imputed, unless otherwise specified.

Baseline assessment is, in general, defined as the last non-missing observation prior to receiving the first dose of any study drug.

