9.3. Clinical Laboratory Data

9.3.1. Laboratory Parameters

Blood and urine samples for the determination of clinical chemistry, hematology, and urinalysis laboratory variables described in Table 9 will be measured according to Schedule of Assessments in Appendix 1.

Lab Category	Lab Parameters
Chemistry	albumin, alkaline phosphatase (ALP), total bilirubin, calcium, chloride, creatinine, glucose, inorganic phosphorus, potassium, total protein, alanine aminotransferase (ALT), aspartate aminotransferase (AST), lactate dehydrogenase (LDH), sodium, blood urea nitrogen (BUN)
Hematology	hemoglobin, white blood cell (WBC), platelet counts, absolute neutrophil count (ANC), absolute lymphocyte count (ALC)
Urinalysis	semiquantitative dipstick: specific gravity, pH, evaluation of glucose, protein, bilirubin, ketones, leukocytes, and hemoglobin microscopic examination, including red blood cell (RBC), white blood cell (WBC), and casts will be performed, if necessary

 Table 9
 Laboratory Categories and Parameters

Lab = laboratory.

For hematology parameters, if absolute counts are not provided, those values will be derived from the differential counts by multiplying differential value with leukocyte value from the same sample. The normal ranges will be left missing in those cases.

Clinical chemistry and hematology assessments will be graded according to NCI CTCAE criteria, Version 5.0 or later. The determination of CTCAE grade for each measurement will be based on the collected laboratory values and will not involve clinical judgement. For laboratory parameters that CTCAE toxicity grade are not available, they will not be included in the analyses in which toxicity grades are reported. Instead, these parameter results will be classified and reported by the low/normal/high based on the laboratory normal reference ranges.

Abnormal Hepatic Laboratory Values

Abnormal hepatic laboratory values are defined in the following categories including any occurrence among all on-treatment, post-baseline assessments including scheduled and unscheduled values.

- Hy's Law:
 - Alanine aminotransferase (ALT) and/or aspartate aminotransferase (AST) > 3x the upper limit of normal (ULN), alkaline phosphatase (ALP) < 2xULN, and total bilirubin ≥ 2xULN
 - Preexisting baseline ALT, AST, OR total bilirubin values above the upper limit of normal, and the patient subsequently presents with:

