9.5.2. Analysis for Electrocardiograms Parameters

For each ECG parameter in Table 11, the number and percentage of patients who met each potentially clinically significant criterion will be summarized.

Investigator's clinical interpretation of the 12-lead ECG results (normal or abnormal) will be tabulated to present shift from baseline to the worst case post-dose during the treatment period. Similarly, a shift table from baseline to the last post-baseline assessment during the treatment period will be generated.

All ECG parameters as collected along with corrected values of QTcF will be included in the data listing. In the listing, the flag of meeting a PCS criterion and the flag indicating investigator's determined abnormality are also included.

G1 Therapeutics

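### SAP 9.5.1 leaves QTcF missing when RR is blank, although heart rate from the same ECG would give RR to within rounding

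*SAP*

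**What the plan says.** SAP section 9.5.1 says the 12-lead ECG "will collect heart rate, PR interval, QRS interval, RR interval, and QT interval". It gives the reason for a central calculation: "Since either QTcF or QTcB could be collected by different study sites". QTcF by Fridericia's formula "will be calculated from the QT and RR (converted from collected ms to sec) intervals", and "if QT and/or RR are missing, the QTcF will be left as missing". No fallback is given in 9.5.1 or 9.5.2.

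Four other places bear on the point:

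- **SAP 9.1** sets the general rule: "Missing safety data will generally not be imputed, unless otherwise specified".
- **SAP 9.3.1** treats hematology differently. Where absolute counts are not provided, "those values will be derived from the differential counts by multiplying differential value with leukocyte value from the same sample".
- **SAP 9.5.2** says "For each ECG parameter in Table 11, the number and percentage of patients who met each potentially clinically significant criterion will be summarized". It also lists all ECG parameters as collected.
- **SAP 4.3 (Table 3) and 9.1** define baseline as the last non-missing value before the first dose. **Protocol 11.3.4** schedules triplicate ECGs at Screening and at three timepoints on each of Days 1 and 8 of Cycle 1.

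**The concern.** Heart rate and RR carry nearly the same information. If RR is blank on a tracing that has QT and heart rate, QTcF can be worked out from fields already in the database, yet the rule sets it to missing.

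QTcF has five criteria in Table 11 and is the only ECG parameter there judged on change from baseline as well as on observed value. Changes in ECG parameters are a secondary safety endpoint (Protocol Table 5). The criteria use the highest or lowest post-baseline value, so one lost post-dose tracing can hide a patient's maximum. Scheduled ECGs stop after Cycle 1 Day 8, so no later scheduled visit can make up for it.

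The hematology rule shows that the SAP accepts same-sample derivation elsewhere. It gives no reason for a stricter rule here.

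**Working it through.** The plan gives no figure to reproduce on this point. The check asks how well heart rate recovers QTcF, whether uncorrected QT covers the gap, and what it takes to lose a patient.

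**1. The derivation.** SAP 9.5.1 gives QTcF = QT / RR^(1/3), with RR in seconds. Substituting RR = 60/HR gives QTcF = QT × (HR/60)^(1/3).

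Example: QT 400 ms and HR 75 bpm give RR = 60/75 = 0.8 s and QTcF = 400 / 0.8^(1/3) = 430.9 ms. Under the current rule this value is missing if RR is blank.

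**2. Error from whole-number heart rate.** Assumption: HR is recorded to the nearest 1 bpm, so it is within 0.5 bpm. The relative error in QTcF is about (1/3) × 0.5/HR. For a true QTcF of 500 ms:

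| HR (bpm) | Largest shift in QTcF (ms) |
|---|---|
| 50 | 1.7 |
| 60 | 1.4 |
| 75 | 1.1 |
| 100 | 0.8 |
| 120 | 0.7 |

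If the baseline and post-baseline values were both derived in this way, the worst case for a change is about 1.7 + 1.7 = 3.4 ms. That is small beside the 30 ms and 60 ms change criteria.

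**3. Error if recorded HR and RR come from different beats.** The documents do not say whether they do. Assumption: measured RR differs from 60/HR by a fraction d. At QTcF 480 ms the shift is 480 × [(1+d)^(-1/3) − 1]:

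| d | Shift (ms) |
|---|---|
| −10% | +17.2 |
| −5% | +8.3 |
| +5% | −7.7 |
| +10% | −15.0 |

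This is the larger source of uncertainty, and the reason a derived value needs a flag.

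**4. Does uncorrected QT cover the gap?** The QT that corresponds to QTcF 500 ms is 500 × (60/HR)^(1/3):

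| HR (bpm) | QT at QTcF 500 ms (ms) | Meets the QT criterion (≥500 ms)? |
|---|---|---|
| 60 | 500.0 | Yes |
| 75 | 464.2 | No |
| 90 | 436.8 | No |
| 100 | 421.7 | No |

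Above 60 bpm, a tracing at the top QTcF threshold does not reach the QT threshold. Table 11 also gives QT no counterpart to the 450 ms and 480 ms thresholds or to the change criteria.

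**5. What it takes to lose a patient.** From Protocol 11.3.4:

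- Pre-dose: Screening (3 tracings) + Day 1 pre-dose (3) = 6.
- Post-dose: Day 1 (2 timepoints × 3) + Day 8 (3 timepoints × 3) = 15.
- Study total: at most 21 × 30 patients = 630 tracings.

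Because baseline is the last non-missing pre-dose value, and SAP 9.5.1 asks for only one non-missing post-dose value, an isolated blank RR does not remove a patient from the change analysis. For a patient with all scheduled ECGs, all 6 pre-dose or all 15 post-dose tracings would have to lack a usable QT and RR pair. An isolated post-dose blank can still hide the maximum.

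**The case against.** The strongest reply is that the gap may never arise. RR is a planned field with its own Table 11 criteria, and nothing in either document says that any site omits it. What SAP 9.5.1 says may vary between sites is the QT correction. Leaving QTcF missing also agrees with the general rule against imputing safety data. Uncorrected QT, the investigator's interpretation and the full listing all remain, and Protocol 11.3.4 separately requires investigator review of ECGs and a manual read of any QTc above 500 msec. Protocol 4.3.3.1 reports no clinically relevant QTc effect at the study dose.

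Most of this stands and limits the size of the point. It does not remove it. Calculating RR from heart rate on the same tracing is a derivation, like the hematology rule, so it does not breach the no-imputation principle. Section 4 of the working shows that QT does not replace QTcF.

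A reader might infer four stronger claims, which the documents do not support:

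- **Heart rate gives RR exactly.** It gives RR only to rounding, and less closely if the two come from different beats.
- **QT data are thrown away.** Only the derived QTcF is lost.
- **Whole patients or sites drop out.** No rate or site pattern of missing RR is given, so any percentage would be invented, and the baseline definition protects against isolated gaps.
- **A site-reported QTcF should be the next fallback.** The SAP says only that sites could supply QTcF or QTcB. Using reported values would bring back the mixed sources that the central calculation is meant to avoid.

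**Conclusion.** The point holds as a small gap in a safety derivation. When RR is blank and QT and heart rate are present, the SAP leaves out a QTcF that can be recovered to within 2 ms at 50 to 120 bpm, assuming that heart rate is rounded to whole beats and reflects the same beats as RR. The loss affects the Table 11 QTcF counts and the post-baseline extreme. Its extent is unknown and may be nil. It has no bearing on the primary endpoint or on any efficacy conclusion, and is worth correcting mainly because doing so costs almost nothing.

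**What to change.** In SAP 9.5.1, replace the missing-value rule with the following:

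> *If RR is missing and ECG heart rate from the same tracing is present, RR (sec) = 60/heart rate. Flag the derived QTcF in the listing, and report the number of QTcF values derived this way and the number still missing. Otherwise QTcF is missing.*

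The cost is one sentence, one line of code, a listing flag and two counts, with no new data. If the SAP is already signed off, its section 1 provides for documenting the change and its rationale in the clinical study report. If no RR is missing, the rule does nothing.

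There is a small downside. Derived values are approximate, so a value close to 450, 480 or 500 ms could fall in a different category, more so if recorded heart rate and RR come from different beats. The flag and the counts let a reader see whether any reported finding depends on a derived value.

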- 12. QT corrected interval using Fridericia's formula (QTcF) >480 msec at screening (confirmed on repeat). For patients with ventricular pacemakers, QTcF >500 msec.
- 13. Uncontrolled ischemic heart disease or uncontrolled symptomatic congestive heart failure (Class III or IV as defined by the New York Heart Association functional classification system).
- 14. Known history of stroke or cerebrovascular accident within 6 months prior to first dose of study treatment.
- 15. Known serious active infection such as, but not limited to, human immunodeficiency virus (HIV) (e.g., viral load indicative of HIV, HIV 1/2 antibodies), Hepatitis B (e.g., Hepatitis B surface antigen reactive or Hepatitis B DNA detected), Hepatitis C (e.g., Hepatitis C ribonucleic acid [quantitative] is detected) or tuberculosis.
- 16. Severe infections within 4 weeks prior to enrollment, including but not limited to hospitalization for complications of infection, bacteremia, or severe pneumonia.
- 17. Other uncontrolled serious chronic disease or psychiatric condition that in the Investigator's opinion could affect patient safety, compliance, or follow-up in the protocol.
- 18. Known hypersensitivity or allergy to irinotecan, SN-38, trilaciclib, or sacituzumab govitecan-hziy or any excipients of the aforementioned medications.
- 19. Prior hematopoietic stem cell or bone marrow transplantation.
- 20. Pregnant or lactating women:
  - a. Women of childbearing potential must have negative serum pregnancy test result within 7 days prior to initiating study treatment.
- 21. Major surgical procedure, open biopsy, or significant traumatic injury within 4 weeks prior to study treatment start, or anticipation of the need for major surgical procedure during the course of the study.
- 22. Received a live, attenuated vaccine within 4 weeks prior to the first dose of study treatment or anticipation that such a vaccine will be required during the study treatment period:
  - a. Influenza vaccination should be given during influenza season only (approximately October through May in the Northern Hemisphere).
- 23. Legal incapacity or limited legal capacity.

G1T28-213

24. Patients who are investigational site staff members directly involved in the conduct of the study and their family members, site staff members otherwise supervised by the Investigator, or patients who are employees of G1 Therapeutics, Inc. directly involved in the conduct of the study.

G1T28-213

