9.3.2. Analysis for Laboratory Parameters

Laboratory data from all central and local laboratories will be included in analyses. Different laboratories are likely using slightly different normal reference ranges, which should not affect the planned analysis since they are all categorical and reported based on CTCAE toxicity grade or relationship to the normal ranges. The default convention for reporting of laboratory units will be standard international (SI) units. If a lab value is reported using an inequality symbol e.g., less than (<) a certain value, or greater than (>) a certain value, the given numeric value will be used in the summary. Data will be presented in listings with their inequality symbol.

For each parameter in the clinical chemistry and hematology laboratory group, respectively, CTCAE toxicity grading is used to classify patients into a toxicity grade from 1 to 5 (where

applicable) for each timepoint assessment. The number and percentage of patients with highest grade during the treatment period will be summarized for each grade from 1 to 4 and Grade 3-4, along with such summary for the value collected at baseline.

For the laboratory parameters that cannot be classified by CTCAE grade, the number and percentage of patients in the categories of treatment-emergent low or treatment-emergent high based on the normal reference range associated with the parameter will be summarized.

The number and percentage of patients in each category of abnormal hepatic laboratory values will be summarized.

Laboratory parameters will be listed by the group of chemistry, hematology, and urinalysis. In the data listing, flags that indicate the corresponding CTCAE grades and the classifications relative to the laboratory reference ranges will be included. In addition, a separate listing will be prepared for patients who met Hy's law, if any.

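### The value-based limits for potentially clinically significant ECG and vital-sign findings take no account of baseline, so the counts mix pre-existing with new abnormality

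*SAP*

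**What the plan says.** **ECG.** SAP Table 11 sets value limits for RR, PR, QRS, QT and QTcF. The text says "The potentially clinically significant ECG findings are defined by the highest/lowest value across all post-baseline assessments" during treatment, "for all parameters except for QTcF, for which both observed values and change scores are used to define the PCS findings". The change column of Table 11 is empty for RR, PR, QRS and QT. For QTcF, the value limits (Index 1 to 3) and the change limits (Index 4 and 5) stand on separate rows. SAP 9.5.2 then states that "the number and percentage of patients who met each potentially clinically significant criterion will be summarized".

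**Vital signs.** SAP 9.4.1 describes the findings as "defined by the highest/lowest value among post-baseline assessments and/or the change from baseline to the highest/lowest observed value". Table 10 puts a value limit and a change limit side by side for systolic pressure, diastolic pressure and heart rate. Weight has only a change limit. SAP 9.4.2 adds: "Number and percentage of patients who meet any PCS criteria for each vital sign parameter as well as for each criterion will be summarized".

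**Entry.** Protocol 7.2, exclusion 12, removes patients with QTcF ">480 msec at screening (confirmed on repeat"), or above 500 msec if they have a ventricular pacemaker. Protocol 7.1 and 7.2 set no numeric limit on PR, QRS, RR, uncorrected QT, blood pressure or heart rate.

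**Laboratory data, for comparison.** SAP 9.3.2 reports parameters without a CTCAE grade "in the categories of treatment-emergent low or treatment-emergent high". For graded parameters it shows a baseline summary alongside the highest on-treatment grade.

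**The concern.** The only input to each value limit is the most extreme post-baseline reading. A patient who enters past the limit and stays there is counted exactly like one who crosses it on treatment.

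The safety endpoint in Protocol Table 5 and SAP Table 1 is change in ECG parameters and vital signs. A count that a patient can enter without changing does not measure that. In a randomized trial a control column would show the background rate. Here there is one column, so a reader of the report could take the whole percentage as arising on treatment.

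**Working it through.** The plan states no figure to reproduce. The check sets the limits against the entry criteria and then illustrates how reliably a pre-existing abnormality is counted.

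**Step 1. Can an eligible patient start past the limit?**

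| Value limit (SAP Tables 10 and 11) | Entry limit (Protocol 7.1, 7.2) | Can start past it? |
|---|---|---|
| QTcF ≥450 | >480 excluded (>500 if paced) | Yes, 450 to 480 |
| QTcF ≥480 | same | Only at exactly 480, or paced at 480 to 500 |
| QTcF ≥500 | same | Only paced at exactly 500 |
| PR ≥210; QRS ≥120 or ≤50; RR >1200 or <500; QT ≥500 or ≤300 | none numeric | Yes |
| SBP ≥180 or ≤90; DBP ≥105 or ≤50; heart rate ≥120 or ≤50 | none numeric | Yes |

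The entry reading is taken at screening, while SAP baseline is the last value before the first dose. Small drift between the two could add an occasional case to the 480 row.

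**Step 2. How often is such a patient flagged?** Protocol 11.3.4 schedules triplicate ECGs before dosing, after trilaciclib and after sacituzumab govitecan on Days 1 and 8 of Cycle 1. Post-baseline this gives 2 + 3 = 5 timepoints, or 5 × 3 = 15 single readings. The SAP does not say whether the extreme is taken over single readings or triplicate means, so both are shown.

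For true QTcF μ, true shift d, SD s of the unit used, and K independent values:

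P(flag at ≥450) = 1 − Φ((450 − μ − d)/s)^K

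The SD (5 to 12 msec) and independence are assumptions. Example with μ = 455, d = 0, s = 12, K = 5: Φ(−0.417) = 0.338; 0.338^5 = 0.004; P = 0.996.

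Ranges over s = 5, 8, 12 and K = 5, 15:

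| True QTcF at entry | No change | Falls 10 | Falls 20 | Falls 30 |
|---|---|---|---|---|
| 455 | 0.996–1.00 | 0.58–1.00 | 0.01–0.81 | 0.00–0.25 |
| 465 | 1.00 | 0.996–1.00 | 0.58–1.00 | 0.01–0.81 |
| 475 | 1.00 | 1.00 | 0.996–1.00 | 0.58–1.00 |

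At a true value of exactly 450 with no change, any SD gives 1 − 0.5^5 = 0.97 or 1 − 0.5^15 > 0.999.

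**Step 3. What does it do to a percentage?** SAP 1.1 gives 30 enrolled. If all were dosed, one patient is 1/30 = 3.3 percentage points. The share already past a given limit is not in the documents. For assumed shares π, the expected count is 30π and P(at least one) = 1 − (1 − π)^30:

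| Assumed share | Expected count | P(at least one) |
|---|---|---|
| 5% | 1.5 | 0.79 |
| 10% | 3 | 0.96 |
| 20% | 6 | 0.999 |

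**Step 4. Does another planned output separate the two?** The ECG shift tables in SAP 9.5.2 use the investigator's normal or abnormal reading, not these limits. The change rows for QTcF and vital signs sit beside the value rows and remove nobody from them. The listings let a reader trace individual patients but leave the tabulated percentage as it is.

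**The case against.** **The SAP follows the protocol.** Protocol 12.4.7.2 allows these findings to be defined either by a post-baseline value or by a change. That stands: this is a weakness of presentation, not a departure from the protocol.

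**Vital signs are ambiguous.** The and/or in SAP 9.4.1 could mean that the value and change limits must both be met, which would bring baseline in. SAP 9.4.2 favors separate counting but does not settle it. This stands as a qualification.

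**Baseline-aware summaries may exist.** Protocol 12.4.7.2 also plans observed values and changes from baseline for ECG and vital signs. SAP 9.4.2 and 9.5.2 do not repeat them, SAP Section 10 records dropping only the laboratory change summaries, and the SAP prevails where the two differ. Their status is unclear. Even if produced, they would not show how many flagged patients started past a limit.

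**Little depends on the counts.** They are descriptive, no test or stopping rule uses them, and the error overstates findings. This stands and keeps the point modest.

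**Stronger readings that the documents do not support:**

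- That a patient past the limit is counted whatever the drug does. A fall of 20 msec from 455 can cut the flag probability to 0.01.
- That patients just under a limit show the same defect. At a true 440 with no change, 15 independent readings with SD 6 to 10 give 0.52 to 0.93. Five triplicate means (SD divided by √3) give only 0.01 to 0.19. Either way, such a patient was not past the limit at baseline.
- That the laboratory section fully solves the problem. For graded parameters it shows baseline beside the worst grade but does not remove pre-existing cases.

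**Conclusion.** The point holds for the value limits on RR, PR, QRS, QT and QTcF and, reading Table 10 with SAP 9.4.2, for those on blood pressure and heart rate. The main exposure is QTcF of 450 to 480, PR of 210 or more, QRS of 120 or more, and the blood pressure and heart rate limits. Eligible patients already past one of these will usually be counted as on-treatment findings without any change. The QTcF rows at 480 and 500 are almost unaffected because of exclusion 12.

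The mixing follows from the definitions alone. Its size does not: it depends on a baseline share that the documents do not give, and the 5% to 20% used above is illustrative. The flag probabilities also rest on an assumed SD and independent readings. No efficacy conclusion is touched. This is a worthwhile improvement because it is nearly free.

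**What to change.** In SAP 9.4.2 and 9.5.2:

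- Keep all patients in the tables. For each value limit, add the number already meeting it at baseline and the number newly meeting it, as a cross-tabulation of baseline against worst post-baseline status.
- For QTcF Index 1, show a shift across the ordered bands (below 450, 450 to below 480, 480 to below 500, 500 or more), so that a move to a lower band is not counted as new. Treat the row at 300 or below separately, since it uses the lowest reading.
- Do not drop patients who meet a limit at baseline. PR, QRS, RR and QT have no change rows, so a patient going from PR 215 to 280 ms would leave the count and real worsening would be hidden.
- State that the value and change limits in Table 10 are counted as separate criteria.

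The baseline readings are already scheduled (Protocol 11.3.4) and baseline is already defined (SAP Table 3 and 9.4.1). The cost is SAP wording, a small programming change and slightly larger tables.
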